The study team member will provide an overview of the study and provide an unsigned copy of the informed consent to the potential participant, allowing ample time to read. If the patient is interested in participating, the study team member will review the informed consent verbally with the participant, answer any questions and obtain a signature on the consent form located in RedCap. If a patient does not want to consent to the study, the study team member will politely inquire rationale behind the refusal and this will be tracked as part of the main outcome related to feasibility. In previous studies, reasons for refusal at this point have included 'too much pain', 'not interested', 'do not want to do follow-up surveys and/or other study procedures' and 'discharged and don't want to wait'.

D. Randomization

After participants have undergone informed consent, the randomization procedure will take place. The investigation will employ a blocked randomization strategy with random assignment of block size of either 4 or 6 participants. Randomization will also be stratified by inclusion for prescription opioid misuse based on a NIDA m-ASSIST score of ≥ 4 for prescription opioid misuse. It is hypothesized that the majority of participants will screen in for illicit opioid use and stratified randomization will be used to ensure balance of participants with prescription opioid misuse given this is an important but likely small population of participants. Participants will be randomized to the following conditions:

- a. Usual Care control condition
- b. ED-LINC 2.0

Study condition will be assigned using the RedCap randomization module which will be programmed prior to study start by a data analyst. After the study team member obtains informed consent, randomization of condition will be performed using RedCap and the participant will be notified of their random assignment.

E. Baseline Interview

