The study team member will next administer the baseline assessment. The additional survey items will be administered via RedCap by the study team member and is anticipated to take an additional 20-30 minutes. Specifically, the study team member administering the survey will enter the responses directly into RedCap or assist the participant with direct data entry. The RedCap application is sponsored by the University of Washington ITHS and is encrypted. The application will be run on an encrypted I-pad using the University of Washington wi-fi network. Participants can complete the baseline survey in the ED during their clinical evaluation or in any inpatient area. The study team members will not delay or interrupt clinical care and the baseline assessment can be stopped and restarted to allow for continuity of clinical care. If the participant is discharged before the assessment is complete, the participant will be offered the chance to continue after discharge outside of clinical space. Importantly, if there are issues with data entry for RedCap (e.g. wi-fi connection, application malfunction) the study team member will be ready to administer the survey using paper and pen and this hard copy of the survey response will be kept as a source file in a locked file cabinet in a locked office per confidentiality procedures. These responses will later be entered into RedCap.

F. Usual Care Condition

Previous investigations at HMC suggest that patients with substance use comorbidity may receive a spectrum of consulting services visits including social work services, psychiatric consultation, inpatient psychiatry consult, rehabilitation psychology consultation, addiction intervention services, pain team consultation services that include MD psychiatric and PhD psychologist providers, spiritual care or other consulting services. Some of these services social work routinely visit patients with substance use concerns. Other services must be generated by a consult request from the clinical team, such as psychiatry consultation. The services provided to participants in the Usual Care condition will be abstracted from the EMR and tracked in RedCap. There is no cost to patients for interacting with the study team members. However, services received from other hospital staff may incur cost to patients as these services will be billed to patients and their insurance per usual billing procedures.

G. ED-LINC Intervention Condition

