Participants randomized to the Intervention Condition will receive 'ED-LINC' which is a multi-component intervention based on the collaborative care framework. It is hypothesized that patients with risk for OUD have fragmented healthcare, might receive opioids from many sources and use the ED for episodic acute healthcare needs and often as an entry point for seeking treatment for OUD. The intervention is built on the hypothesis that patients with risk for opioid use disorder (OUD) from illicit opioid use or prescription opioid use will benefit from coordinated care. There is no cost to patients for interacting with the study team members. However, services received from other hospital staff may incur cost to patients as these services will be billed to patients and their insurance per usual billing procedures. Therefore all components of ED-LINC aim to improve coordination of care and decrease care fragmentation. Consistent with other ED-based interventions, there is an emphasis on initiating services and then linking to outpatient service providers. ED-LINC will include **1)** A brief negotiated interview at the bedside with an emphasis on motivation to link to services **2)** Pharmacotherapy including a discussion of opioid safety, take-home naloxone and initiation of buprenorphine from the ED for participants that are interested and eligible; **3)** Longitudinal care management which will proceed for 3-months; and **4)** Care plan in the Emergency Department Information Exchange (EDIE) system. Linking all these elements will be weekly supervision and case conferences attended by the research assistant, study PI and study psychiatrist along with other relevant team members as required in addition to a study cell phone which will be used by study team members to provide care management. The study cell phone will be answered as soon as possible by study team members with messages/texts returned within 1-2 hours during 9-5 M-F and messages/texts returned within 12-24 hours overnight and on weekends. All elements of ED-LINC will be discussed in further detail below.

Brief Negotiated Interview

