Consistent with the guidelines of collaborative care, the RC will receive supervision from the study physicians. The study PI, [name] and study psychiatrist, [name] will be available to discuss all new ED-LINC participants at the time of enrollment and regularly scheduled supervisory meetings will be held with all study team members weekly to every-other week depending on case load and availability. During these meetings, the RC will lead a discussion of all newly enrolled participants as well as any active participants. A discussion of relevant assessments will take place for all discussed participants to tailor further care management and linkage to services. Content of these discussions will be documented in RedCap. All members of the team attending the supervision and case conference meetings will have obtained human subjects training prior to participating.

Cell Phone

The study [contact]) will be provided to all participants in the ED-LINC intervention. Specifically, after the baseline interview participants randomized to ED-LINC will be provided with the cell phone number and notified that they can call or text this number with any concerns during the course of their intervention time. The cell phone will be covered by the study RA/RC or study PI from 9a-5p M-F and by one of the study physicians on evenings, nights and all day weekends and holidays. All efforts will be made to answer the call during business hours and response to calls and text during business hours will be within 1-2 hours. Efforts will be made to be timely after hours as well. Participants will be notified that calls and texts that occur after hours, on weekends and on holidays can be anticipated to be answered within 24 hours. All interactions with participants on the study cell will be tracked in research logs and notes captured in RedCap.

H. Intervention Training and Supervision

1. Training

The study research assistant will receive training in Motivational Interviewing in order to perform the Brief Negotiated Interview (BNI) with fidelity. Specifically the RA will attend a 1-day workshop specific to Motivational Interviewing techniques in substance use and will complete practice sessions (e.g. standardized patients) and receive feedback on the core principles of BNI. The RA will receive at least 16 hours of training which is consistent with other studies conducting similar interventions.

2. Supervision

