Appendix C. ED-LINC PATIENT SAFETY SUICIDALITY PROTOCOL

This protocol addresses potential subject suicidal risk given that suicidal ideation is common among the patient population. Suicidal risk is indicated by subject self-report of suicidality or suicidal behavior. The following procedure addresses positive responses to the PHQ-9 or other reports of suicidality by study patients. Importantly, patients with a primary chief complaint of suicidal ideation or in the ED for treatment after a suicide attempt are not eligible for participation.

The study team collects patient-reported outcomes at baseline, prior to randomization, and at a series of post-randomization follow-up assessments according to a pre-determined schedule (1, 3, 6 months after the baseline assessment). These assessments include questions about patient psychological and emotional distress. Each assessment includes a question about having thoughts of self-harm or being better off dead on the Patient Health Questionnaire 9 item (PHQ-9) depression measure. The PHQ-9 question #9 asks patients “how often have you been bothered by thoughts that you would be better off dead or of hurting yourself in some way?” The response choices are: 0 = Not at all, 1 = A little of the time, 2 = More than half the time, 3 = Nearly all the time.

Work by Gregory Simon et al. (2013) in a general medical setting documented a low risk of completed and attempted suicide by subjects that endorsed a “1” on the PHQ-9 item #9 question; of those that responded with a “1”, approximately 1% attempted suicide and 0.08% completed suicide. The rates of attempts and completed suicide did increase with higher scores on the PHQ-9 item #9; however, the absolute risk remained relatively low; of those that endorsed a “3” on the PHQ-9 item #9, 4% attempted suicide over the course of a year. The low risk of suicide completion associated with a positive PHQ-9 led the study team to include a follow-up question to directly assess whether patients are currently having thoughts of suicide.

Suicidality or suicidal behavior discovered at baseline

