If a patient indicates anything greater than 0, “Not at all,” on PHQ-9 item #9, the interviewer will ask a Yes/No follow-up question, labeled #9a *“Over the past two weeks, have you had any plans to harm yourself or take your own life?”* (or “in the past month” for follow-up interviews). If the patient endorsed a “Yes” to item 9a, following completion of the assessment (or earlier if needed), the interviewer will provide the patient with a suicide crisis line and call the study’s 24/7 cell phone after the assessment to inform the study clinical team about the patient. A member of the clinical team will assess the patient either in person at the hospital or via phone to assess risk and safety plan. If there is imminent danger of self-harm the interviewer or member of the study team will inform the participant of the need to inform hospital staff. Of note, if during the baseline interview or during the initial follow-up by the study team to baseline interview responses the study team learns that the subject’s initial injury was due to a suicide attempt, the subject will be withdrawn by the study team per the exclusion criteria. If the study team learns that the initial injury was due to a suicide attempt at any other point during the subject’s trial participation, the subject will be eligible to continue study participation.

If the patient reports a “No” to item 9a, but is otherwise positive on PHQ-9 item #9, the interviewer will provide the patient with a suicide crisis line (see below). A member of the clinical team will visit the patient in the hospital to assess risk and discuss suitable safety planning.

Should the patient inform the interviewer that they have current suicidal ideation and intent outside of the interview questions; the interviewer will inform hospital staff. If the patient

indicates they are having suicidal thoughts at any other time during the baseline assessment, even if the response to the PHQ-9 item 9 is 0, the recruiter will inform the clinical team following completion of the baseline assessment who will, in turn, follow the aforementioned procedures according to randomization assignment.

Suicidality or suicidal behavior discovered at follow-up

The following protocol is initiated if a subject indicates anything greater than 0, “Not at all,” on PHQ-9 item #9.

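### Protocol III.D–E discloses the arm before the baseline interview, while Appendix C puts baseline first; the SAP does not say which order was used, so baseline TLFB may be arm-aware

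*Protocol*

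**What the plan says.** The protocol (version of November 12, 2018) places the baseline assessment relative to randomisation in two incompatible ways.

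- **III.D, Randomization.** Once consent is obtained, "randomization of condition will be performed using RedCap and the participant will be notified of their random assignment".
- **III.E, Baseline Interview**, the section that follows: "The study team member will next administer the baseline assessment". The order is therefore consent, randomisation, disclosure, baseline.
- **Appendix C**, introducing the suicidality procedure: "The study team collects patient-reported outcomes at baseline, prior to randomization".

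Protocol VII.B.2 (Substance Use and TLFB) has past 30-day use recorded on a calendar at baseline and at every follow-up. It does not say on which date the 30 days end. Protocol VI.B.4 restricts access to intervention logs so that the follow-up interviewers stay blinded. No blinding is described for whoever takes the baseline.

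The SAP (Secondary Outcome Measures, Substance Use) sums days of illicit opioid use per participant at baseline and each follow-up, and reports the mean and standard deviation by arm at each time. It then describes a regression with intervention and TLFB timepoint among its terms. It is silent on whether baseline was taken before or after randomisation.

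**The concern.** A baseline measure is useful for comparing arms because assignment cannot have influenced it. That is secure for a self-reported measure only if it is taken before the participant learns the arm. TLFB depends on recall and on willingness to report illicit use. A participant who has just been told they will, or will not, receive a care-management programme for opioid use may report differently. An interviewer who knows the arm may also probe differently.

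At stake is the reading of the baseline row in the substance-use table and of anything computed against it, such as change from baseline or a model that includes baseline as a timepoint. A difference between arms at baseline could then be chance imbalance or a reporting effect, and the reader could not tell which. The reader also cannot tell whether the question arises at all, because the two protocol passages give opposite answers.

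**Working it through.** The documents give no figure to reproduce, so the check is to set side by side every statement that orders baseline against randomisation, and then trace where baseline TLFB is used.

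**1. Which order?**
- III.D then III.E: randomise, disclose, then baseline.
- Appendix C, opening description: baseline, then randomise.
- III.G, Cell Phone: "after the baseline interview participants randomized to ED-LINC will be provided with the cell phone number". This fits either order, since in both the number is handed over once baseline is done and the arm is known.
- Appendix C, suicidality found at baseline: the clinical team is told after the assessment is complete, "who will, in turn, follow the aforementioned procedures according to randomization assignment". This also fits either order.
- SAP: no statement.

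One place supports each order, two are neutral, and nothing settles it. All of these are current text, so this is not a difference between a change log and the plan.

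**2. Who would know the arm under III.D–E?** The participant would, because III.D says so. The interviewer may: III.C–E use the same generic staff term for consent, randomisation and baseline. Protocol VI.B.3 also names the research coordinator as a possible collector of patient-reported outcomes, and III.G has the research coordinator deliver the intervention. Nothing separates the roles at baseline. Under the Appendix C order neither would know.

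**3. What uses baseline TLFB?**
- Baseline arm means and standard deviations (SAP): yes.
- The regression with intervention and timepoint (SAP): only if baseline rows are included, which the SAP does not say.

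**4. What does not depend on the order?**
- Primary feasibility outcomes (refusal, completion, process, appropriateness, satisfaction, perceived coordination): none uses baseline TLFB.
- The NIDA m-ASSIST score: taken at the verbal screen (III.B), before consent, so eligibility and the stratification factor are unaffected.
- Follow-up arm means taken alone: participants know their arm by follow-up under either order.

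**5. Size.** Neither document gives an expected TLFB mean, a standard deviation or any estimate of how disclosure changes reporting. Neither magnitude nor direction can be calculated.

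**The case against.** The strongest reply is that III.C–E is the operative procedure and Appendix C contains one loose introductory phrase. The appendix is loosely edited elsewhere: it words the follow-up suicidality item in two ways and refers to a DSMB that Protocol V does not set up. On this reading the defect is a single wrong clause. That is reasonable, though not proven. But it resolves the contradiction in favour of the order that creates the problem: if III.D–E governs, baseline TLFB was collected after disclosure.

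A second reply is that little rests on it. Outcomes are mainly descriptive, Protocol II.B.1 says the study is not powered for a difference, and Protocol VIII says effect sizes are not being measured. This stands, and it is why the point is minor. It does not remove the point, because the SAP still reports baseline TLFB by arm and describes a model with an intervention term.

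Some stronger readings are tempting but not supported:

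- **Baseline contaminated by treatment.** III.E allows interruption, and on discharge "the participant will be offered the chance to continue after discharge outside of clinical space". The intervention includes "A brief negotiated interview at the bedside with an emphasis on motivation to link to services". A reader might infer that baseline could follow intervention contact or run days late. The text names a place, not a delay. No passage describes a baseline completed days later, and the planned sequence puts baseline before the intervention.
- **Bias in PHQ-9.** It is also collected at baseline, but no stated outcome or analysis uses it. In Appendix C it triggers safety actions.
- **Post-randomisation exclusions created by III.D–E.** Appendix C says that if the presenting injury proves to be a suicide attempt, "the subject will be withdrawn by the study team per the exclusion criteria". It allows this also on facts learned in the team's initial follow-up of baseline responses, so such a withdrawal could come after randomisation under either order.

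**Conclusion.** The contradiction is established from the text alone. What follows from it is conditional: if the III.D–E order was used, baseline TLFB is open to arm-aware reporting by the participant and possibly by the interviewer; if the Appendix C order was used, it is not. The documents do not show that III.D–E was followed, nor that any bias occurred.

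A reader might go further and conclude that the randomised comparison itself is compromised. It is not: assignment comes after eligibility screening and consent, and the order of the baseline interview does not alter who is in which arm. The effect is limited to the secondary substance-use outcome, through the baseline means and possibly the model, and its size and direction are unknown. Severity is minor. Confidence is high for the conflict, but not for any actual distortion of results.

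**What to change.** **If anyone is still to be randomised.** Reconcile III.D–E with Appendix C on one order, with baseline TLFB completed before the RedCap randomisation step and the remaining baseline items allowed afterwards. Define the baseline 30-day window to end on or before the day of assignment. The cost is a wording amendment and moving one RedCap step. The real downside is that some patients discharged early would not reach randomisation. Their number is unknown. They should be counted in the enrolment feasibility outcome, as III.C already lists unwillingness to wait at discharge among past reasons for refusal.

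**For participants already randomised:**
1. Keep everyone in the assigned arm.
2. State which order was used, from RedCap records or the TLFB hard copy where these show the time of collection. Protocol VII.B.2 has the calendar completed on paper and then transferred, so a RedCap timestamp alone may show entry rather than interview.
3. Wherever baseline TLFB taken after disclosure is reported or modelled, footnote it as post-randomisation and open-label.

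The SAP is dated September 2021 and is partly in the past tense, so probably only these reporting steps apply: one sentence and one footnote. They tell the reader what the baseline is; they cannot measure or remove a reporting effect in data already collected. Settling the order also keeps the conflict out of the later ED-LINC studies that this pilot is meant to inform. No change to the Appendix C safety procedures is proposed.

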Patient-reported outcomes will be assessed at 1, 3 and 6 months after the ED visit. Length of the follow-up interviews varies and is estimated that the shortest interview may take about 15 minutes to complete and up to 60 minutes to complete the longest follow-up assessment depending on subject answers. Subjects will be remunerated for their time. The study team will be flexible with regard to completion method of the follow-up interviews. The study team intends to complete follow-up interviews with subjects primarily in-person at Harborview Medical Center or other convenient public location or over the phone. Responses will be entered into REDCap. If scheduling time with an interviewer is difficult, a subject may also have the option of completing the follow-up assessment through the encrypted REDCap app or web-based platform, or by another preferred method (e.g., faxed interview, hardcopy mailed to their residence). If a subject is completing the assessment on their own, the interview form (e.g., PDF, hardcopy, REDCap) would not include their name or any directly identifying information. Subjects will be given explicit instructions on certain assessments such as the timeline follow back (TLFB) in order to complete this with accuracy and without RA/RC assistance. Subjects will be reminded they should complete the interview in a private space where no one else can have access or see the interview.

Some subjects will have difficulty completing the entire interview, such as due to fatigue. The study team will allow for patients who are unable to tolerate a full-length interview the option of completing an interview over multiple sessions

Prior observations from the study team's effectiveness implementation spectrum investigations suggest flexibility is also required with regards to the timing of outcome assessments. Biostatistical considerations related to power encourage obtaining follow-up assessments, even if the actual assessment date deviates from the planned outcome assessment point. The study team will attempt follow-up on the appropriate date (e.g., within 30 days for the one month follow-up interview) but understand that flexibility on timing of followup interviews are needed.

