Past 30-day substance use will be obtained at baseline and every follow-up assessment and calendar will be used to track substance use on specific days. Prior to performing this assessment, members of the study team will receive training on TLFB methods including a webinar published by NIDA, review of the methods with current NIDA CTN project coordinators that have performed these assessments for a variety of substances in a variety of settings including the ED and will practice obtaining this data with practice participant encounters. This training will be completed prior to study start to ensure accuracy of obtaining this data. Episodic shadowing by study PI will be done to ensure there isn't drift of accuracy in data collection. TLFB data will be captured on a hard copy calendar and transferred to RedCap by study staff. The hard copy will not contain any PHI and be labeled with a study ID and will be kept in a locked cabinet in a locked

office. At least 25% of these forms will be double-entered into RedCap to ensure accuracy of data entry.

- **Health Care Utilization**

Emergency department (ED) utilization will be assessed throughout the duration of the trial using either the UW EMR system (e.g., the UW Amalga data repository) or the Emergency Department Information Exchange (EDIE) web-based platform on an approximately monthly basis. Additionally, EDIE data will be pulled for all consented patients to capture all ED visits, inpatient visits and any available outpatient visits from five years before enrollment up to five years after enrollment in the trial.

- **ED-LINC Intervention and Usual Care**

The study team will document ED-LINC intervention activities in REDCap. These notes are not static and are modifiable over the course of the trial. For instance, information may be added or modified as a consequence of supervision discussion. The study team will review documentation during team meetings and case conference supervisions and update notes as needed to provide the most complete and accurate picture of what transpired. The data logging tool in REDCap allows administrators to track these types of historical changes. REDCap records the date, time, username of the person logged in at that time, the type of event and the changes that were made. This audit trail in the data logging tool stores every entry/change throughout the life of the database which will help the study team check completeness of intervention data.

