Follow-up Completion Rates were calculated for each followup timepoint and were calculated as the number of participants that completed follow-up divided by the total number of participants randomized to each arm of the trial. The 6-month followup completion rate is shown as the number of participants that completed the 6-month self-report interview divided by the number of participants randomized to each arm.

ED-LINC Intervention and usual Care process Outcomes were determined from extensive research notes. Specifically the EDLINC interventionist conducted a process validity assessment and documented the number of unique ED-LINC elements completed for each participant in the intervention.

Implementation Appropriateness was calculated by providing this validated self-report measure to each participant randomized to the ED-LINC assessment. Results were dichotomized to calculate the frequency of participants who 'agreed' or 'completely agreed' that the intervention was 'applicable' and 'seemed like a good match' to document appropriateness.

Satisfaction was calculated using a validated satisfaction questionnaire and provided to all participants at six-months. Each participant will complete the questionnaire and their results will be summed. The median and IQR range will be calculated for participants in each group that complete the assessment.

Perception of Care Coordination will be done using questions from a validated scale. The Wilcoxon Rank Sum test will be used to determine if there are significant differences between groups.

Secondary Outcome Measures

Substance Use

Substance use will be measured using the timeline follow back procedure which is a validated calendar method to determine days of use in a certain calendar period. First, we will sum days of use of illicit opioid use in 30 days at baseline and each followup period for each participant. The mean days of use/30 days with an associated standard deviation will be calculated at each time-period for both the ED-LINC intervention and the usual care control groups.

Next, we will evaluate variance of the data and test model fit on unadjusted data using different distributions. Given previous work, we anticipate the data to be skewed and zero-inflated. Thus, we hypothesize that we may use a normal Gaussian, Poisson or negative binomial distribution.

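### The plan does not prevent days before enrolment from being counted in the 1-month timeline follow-back outcome when that interview is held before day 30

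*Protocol*

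**What the plan says.** Interview timing is in the Protocol, section III, under Follow-up Interviews. The schedule is "Patient-reported outcomes will be assessed at 1, 3 and 6 months after the ED visit". The team tries to interview on the right date, with "within 30 days for the one month follow-up interview" as the example. It wants the assessment done "even if the actual assessment date deviates from the planned outcome assessment point" and adds that "flexibility on timing of followup interviews are needed". No earliest or latest date is given, and the example does not say what the 30 days are counted from. Appendix C uses a different anchor for the schedule: "1, 3, 6 months after the baseline assessment".

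The recall period is in the Protocol, section VII.B, under Substance Use and TLFB: "Past 30-day substance use will be obtained at baseline and every follow-up assessment". The data are day by day, since a "calendar will be used to track substance use on specific days".

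The SAP (Secondary Outcome Measures, Substance Use) adds up illicit opioid use days in 30 days for each participant at baseline and at each follow-up. Then "The mean days of use/30 days with an associated standard deviation will be calculated at each time-period". It states no cut at the randomisation date and no denominator other than 30.

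**The concern.** A fixed 30-day look-back measures the post-randomisation period only if at least 30 days have passed since enrolment. If the 1-month interview is earlier, part of the window lies before enrolment. ED-LINC cannot have changed those days, and the baseline TLFB normally counts them as well. The 1-month value then mixes outcome with baseline.

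This is more than a missing detail. The SAP's stated rule, applied exactly to an early interview, gives a value that does not describe follow-up. The 1-month assessment is also the first at which linkage to treatment could show. The SAP's regression includes TLFB timepoint, so affected values would enter the model as well as the descriptive means.

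**Working it through.** The documents give no figure to reproduce here, so the check is arithmetic on the windows.

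**Inputs**
- Recall length: 30 days (Protocol VII.B; SAP, Substance Use).
- Interview day d, counted from enrolment. The ED visit and enrolment are taken as the same day, day 0 (assumption).
- Window convention: the 30 dates ending on the interview day, that is, days d − 29 to d (assumption). If the window ends the day before the interview, each non-zero count below rises by one, and an interview on day 30 then includes day 0.

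**Overlap for one interview**

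Days on or before day 0 = max(0, 30 − d). Share = that number / 30.

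| Interview day | Days on or before day 0 | Share of window | Factor d/30 (maximum 1) |
|---|---|---|---|
| 30 or later | 0 | 0% | 1.00 |
| 29 | 1 | 3.3% | 0.97 |
| 28 | 2 | 6.7% | 0.93 |
| 25 | 5 | 16.7% | 0.83 |
| 21 | 9 | 30.0% | 0.70 |
| 14 | 16 | 53.3% | 0.47 |

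**Effect on the arm difference**

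Let δ be the true difference in daily probability of use, constant from day 0 (assumption). Before enrolment the expected difference is zero, because the arms are randomised. With the same d < 30 in both arms (assumption), the expected difference in the 30-day sum is d × δ + (30 − d) × 0 = dδ. A full post-enrolment window would give 30δ. The ratio is d/30.

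If timing differs by arm, the direction is not fixed. Take no treatment effect, daily use p0 before and p1 after enrolment in both arms, and interview days dA and dB, both below 30. Each arm's expected sum is (30 − d)p0 + d p1, so the spurious difference is (dA − dB)(p1 − p0). It can have either sign.

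**Average overlap under assumed spreads of interview days**

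The documents report no interview dates. With days spread uniformly:
- Days 23 to 30: (7 + 6 + … + 0)/8 = 28/8 = 3.5 days (11.7%).
- Days 23 to 37: 28/15 = 1.87 days (6.2%). Seven of the 15 possible days (47%) overlap.
- Days 1 to 60 (30 days either side of day 30): 435/60 = 7.25 days (24.2%). Of the 60 possible days, 29 (48%) overlap.
- Days 30 to 60 (late only): 0.

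**Later assessments**

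Taking 3 and 6 months as days 90 and 180, an interview held 30 days early falls on day 60 or day 150. The overlap max(0, 30 − d) is 0 in both cases.

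**The case against.** A reader might infer that the protocol requires the 1-month interview within 30 days of the ED visit. Early interviews would then be the norm, and pre-enrolment use would routinely be counted as outcome. The documents do not support this. The example names no starting point. It illustrates an appropriate date that the same section places 1 month after the visit, and it may mean closeness to that date. If it allows only later dates, there is no overlap.

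The practical worry in the documents is also lateness rather than earliness: unstable phone numbers, participants out of reach for months, and incarceration (Protocol III, Patient Tracking and Follow-up Interviews). Nothing suggests that interviews in the second or third week were expected. An interview one or two days early affects only 3% to 7% of the window.

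The point is also small in scope. It concerns one of three follow-up times for a secondary outcome, and the protocol says that the pilot has no power for between-arm differences. The primary feasibility outcomes do not use TLFB.

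A constant effect from day 0 is questionable too, since the intervention works partly by linking people to care over three months.

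All of this limits the size and certainty of the problem. It does not supply the missing rule: neither document sets an earliest 1-month date or removes pre-enrolment days from a follow-up window.

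**Conclusion.** The plan permits pre-enrolment days in the 1-month TLFB outcome and does not guard against them. It does not show that this happened.

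For an interview on day d < 30, 30 − d of the 30 days precede follow-up: 7% at day 28 and 17% at day 25. The attenuation factor d/30 rests on a constant effect from day 0 and similar timing in both arms. With unequal timing the bias could go either way. That is possible, because only ED-LINC participants have regular care-management contact.

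Interviews at day 30 or later are unaffected under the window convention used here, and so are the 3- and 6-month assessments. The frequency of early interviews cannot be determined from the documents. This is a minor point, worth acting on because the correction is cheap and, with day-level data, can still be made.

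**What to change.** Add to the SAP, under Substance Use, wording to this effect:

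> For follow-up assessments only, TLFB days on or before the randomisation date are excluded. Observed days are the remaining days in the 30-day window. Descriptive tables give 30 × use days / observed days. Poisson and negative binomial models use the raw count of use days with log(observed days) as an offset. A Gaussian model uses the rescaled rate, without an offset. The baseline TLFB is unchanged.

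Three details matter:
- The exclusion must be limited to follow-up, because applied to every assessment it would delete the baseline window.
- Rescaling and the offset must not be combined, since that adjusts twice for exposure.
- The SAP should say whether the 30-day window includes the interview day.

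Also report the distribution of 1-month interview days by arm. If none falls before day 30, the reader can see that the issue did not arise. State as well which date the follow-up schedule is counted from, since the protocol and its Appendix C differ.

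Setting an earliest interview date is probably too late: the SAP is dated September 2021 and describes the trial largely in the past tense.

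The cost is a few sentences and a date filter. The documents do not say whether individual dates or only totals were entered in REDCap. If only totals were entered, the dates for early interviews would have to be read from the retained paper calendars. Early interviews contribute slightly fewer observed days, so their rates are somewhat noisier.
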